4.2 Registration Process for DF/HCC Institutions

DF/HCC Standard Operating Procedure for Human Subject Research Titled *Subject Protocol Registration* (SOP #: REGIST-101) must be followed.

4.3 General Guidelines for Other Investigative Sites

See Appendix B Section 3.7 (DF/HCC Multi-Center Data and Safety Monitoring Plan) for complete registration procedures.

4.4 Registration Process for Other Investigative Sites

See Appendix B Section 3.7 (DF/HCC Multi-Center Data and Safety Monitoring Plan) for complete registration procedures.

5. TREATMENT PLAN

This is a pilot surgical trial to evaluate early immunologic pharmacodynamic parameters for the PD-1 checkpoint inhibitor, pembrolizumab (MK-3475), in patients with surgically accessible recurrent/progressive glioblastoma. The principle goal of this study is to understand, in surgically resectable recurrent/progressive GBM, if neoadjuvant pembrolizumab elicits a systemic immunologic response, a tumoral immunologic response and toxicity and if that response can be correlated with other non-invasive measures of pembrolizumab bioactivity (tumor, blood, imaging, and clinical outcomes). The study includes 2 stages, in the first stage (**Stage 1**), for optimal understanding of the effect of the drug on tumor tissue patients will be randomized in to Group A or Group B. In the second stage (**Stage 2**), additional patients will be enrolled to an expansion arm of Group A only to specifically study the effect of the drug on cell cycle/cancer proliferation related genetic signature.

Stage 1:

Groups A and B: Patients will be randomly assigned to either group A or B with a 1:1 randomization ratio prior to surgery. Patients in all groups will receive the study drug pembrolizumab after tumor resection. Only Group A will receive a single infusion of pembrolizumab of 200mg 14± 5 days prior to surgery (when scheduling, please keep in mind that the two pre-surgical plasma samples should be drawn greater than 10 days apart - see Table 6 for full details). Group B will not receive study drug prior to surgery. **This randomization scheme should not negatively impact study accrual and will provide an invaluable control cohort for PD evaluations.**

Group A: Neoadjuvant/adjuvant evaluation: Fifteen eligible patients will receive a single infusion of pembrolizumab of 200mg 14± 5 days prior to scheduled surgical resection for

recurrent/progressive glioblastoma (when scheduling, please keep in mind that the two pre-surgical plasma samples should be drawn greater than 10 days apart - see Table 6 for full details). Tumor samples will be obtained at time of surgery. The tissue from this surgery (fresh, frozen and FFPE) and the archived tissue from the archived tissue from the most recent surgery prior to registration revealing glioblastoma (FFPE) will be processed so as to best achieve the primary, secondary and exploratory PD objectives. After recovery from surgery (once participant has recovered from surgery, but no more than 35 days following surgery), patients will resume Q 3 week pembrolizumab at 200mg IV until tumor progression or adverse event requiring discontinuation of study drug. Blood samples will be obtained as pharmacodynamic markers throughout the study. Dose holds and symptomatic management will occur based upon preset adverse event determination. DLTs will not be determined. The toxicity evaluation period will begin with registration and extend to 30 days after last treatment day. Patients will be followed for MRI changes, clinical exam and steroid doses from the registration period and extend to the second progression. After second progression, patients will be followed every 3 months for vital status until death.

Group B: adjuvant evaluation: Fifteen eligible patients will not receive study drug prior to scheduled surgical resection for recurrent/progressive glioblastoma. The two required pre-surgical plasma samples should be drawn greater than 10 days apart - see Table 6 for full details). Tumor samples will be obtained at time of surgery. The tissue from this surgery (fresh, frozen and FFPE) and the archived tissue from the most recent surgery prior to registration revealing glioblastoma (FFPE) will be processed so as to best achieve the primary, secondary and exploratory PD objectives. After recovery from surgery (once participant has recovered from surgery, but no more than 35 days following surgery), patients will begin Q 3 week pembrolizumab at 200mg IV until tumor progression or adverse event requiring discontinuation of study drug. Blood samples will be obtained as pharmacodynamic markers throughout the study. Dose decreases and symptomatic management will occur based upon preset adverse event determination. DLTs will not be determined. The toxicity evaluation period will begin with registration and extend to 30 days after last treatment day. Patients will be followed for MRI changes, clinical exam and steroid doses from the registration period and extend to the second progression. After second progression, patients will be followed every 3 months for vital status until death.

Stage 2:

Group A expansion only: For this stage of the study, 25 additional patients will be enrolled to Group A only with a goal of 20 evaluable patients.

Expansion of Group A: Neoadjuvant/adjuvant evaluation: An additional 20-25 patients will receive a single infusion of pembrolizumab of 200mg 14± 5 days prior to scheduled surgical resection for recurrent/progressive glioblastoma (when scheduling, please keep in mind that the two pre-surgical plasma samples should be drawn greater than 10 days apart - see Table 6 for full details). Tumor samples will be obtained at time of surgery. The tissue from this surgery (fresh, frozen and FFPE) and the archived tissue from the archived tissue from the most recent surgery prior to registration revealing glioblastoma (FFPE) will be processed so as to best achieve the primary, secondary and exploratory PD objectives. After recovery from surgery (once participant has recovered from surgery, but no more than 35 days following surgery), patients will resume Q 3 week pembrolizumab at 200mg IV until tumor progression or adverse

event requiring discontinuation of study drug. Blood samples will be obtained as pharmacodynamic markers throughout the study. Dose holds and symptomatic management will occur based upon preset adverse event determination. DLTs will not be determined. The toxicity evaluation period will begin with registration and extend to 30 days after last treatment day. Patients will be followed for MRI changes, clinical exam and steroid doses from the registration period and extend to the second progression. After second progression, patients will be followed every 3 months for vital status until death.

The investigator shall take responsibility for and shall take all steps to maintain appropriate records and ensure appropriate supply, storage, handling, distribution and usage of trial treatments in accordance with the protocol and any applicable laws and regulations.

5.1 Trial Treatments

The treatment to be used in this trial is outlined below. Each treatment cycle will be 6 weeks (42 days).

Table 2 Trial Treatment

Drug	Dose/ Potency	Dose Frequency	Route of Administration	Regimen/Treatment Period	Use
Pembrolizumab	200 mg	Q3W	IV infusion	Days 1 and 22 of each 6-week (42 day) cycle	Experimental

5.2 Dose Selection/Modification

Dose Selection

The rationale for selection of doses to be used in this trial is provided in Section 2.3.2 – Background and Rationale.

Details on preparation and administration of pembrolizumab (MK-3475) are provided in the Pharmacy Manual.

Dose Modification

No dose reductions (in dose or frequency) are permitted. Only dose holds are permitted per protocol. Treatment may be held for up to 12 weeks (84 days) from last dose.

Adverse events (both non-serious and serious) associated with pembrolizumab exposure may represent an immunologic etiology. These adverse events may occur shortly after the first dose or several months after the last dose of treatment. Pembrolizumab must be withheld for drug-related toxicities (considered at least possibly related to study treatment) and severe or life-threatening AEs as per Table 3 below. If a participant experiences a toxicity unlikely or unrelated to treatment

with pembrolizumab, but may still warrant a hold or reduction of study drug for safety, discussion and writing approval by the Overall Principal Investigator and Study Sponsor, [name], is recommended but not required.

See Section 5.7 for supportive care guidelines, including use of corticosteroids.

Table 3 Dose Modification Guidelines for Drug-Related Adverse Events

Toxicity	Hold Treatment For Grade	Timing for Restarting Treatment	Treatment Discontinuation
Diarrhea/Colitis	2-3	Toxicity resolves to Grade 0-1.	Toxicity does not resolve within 12 weeks of last dose or inability to reduce corticosteroid to 10 mg or less of prednisone or equivalent per day within 12 weeks.
	4	Permanently discontinue	Permanently discontinue
AST, ALT, or Increased Bilirubin	2	Toxicity resolves to Grade 0-1	Toxicity does not resolve within 12 weeks of last dose.
	3-4	Permanently discontinue (see exception below) ¹	Permanently discontinue
Type 1 diabetes mellitus (if new onset) or Hyperglycemia	T1DM or 3-4	Hold pembrolizumab for new onset Type 1 diabetes mellitus or Grade 3-4 hyperglycemia associated with evidence of beta cell failure.	Resume pembrolizumab when patients are clinically and metabolically stable within 12 weeks of last dose.
Hypophysitis	2-4	Toxicity resolves to Grade 0-1. Therapy with pembrolizumab can be continued while endocrine replacement therapy is instituted	Toxicity does not resolve within 12 weeks of last dose or inability to reduce corticosteroid to 10 mg or less of prednisone or equivalent per day within 12 weeks.
Hyperthyroidism	3	Toxicity resolves to Grade 0-1	Toxicity does not resolve within 12 weeks of last dose or inability to reduce corticosteroid to 10 mg or less of prednisone or equivalent per day within 12 weeks.
	4	Permanently discontinue	Permanently discontinue
Hypothyroidism	2-4	Therapy with pembrolizumab can be continued while thyroid replacement therapy is instituted	Therapy with pembrolizumab can be continued while thyroid replacement therapy is instituted.
Immune system disorders - Other: Guillain-Barre syndrome - Any Grade		Permanently discontinue	Permanently discontinue
Infusion Reaction	2 ²	Toxicity resolves to Grade 0-1	Permanently discontinue if toxicity develops despite adequate premedication
	3-4	Permanently discontinue	Permanently discontinue
Myocarditis	3	Toxicity resolves to Grade 0-1	Toxicity does not resolve within 12 weeks of last dose
	4	Permanently discontinue	Permanently discontinue
Myositis	3	Toxicity resolves to Grade 0-1	Toxicity does not resolve within 12 weeks of last dose
	4	Permanently discontinue	Permanently discontinue
Neuropathy (peripheral motor or sensory)	3	Toxicity resolves to Grade 0-1	Toxicity does not resolve within 12 weeks of last dose
	4	Permanently discontinue	Permanently discontinue
Pancreatitis	3	Toxicity resolves to Grade 0-1	Toxicity does not resolve within 12 weeks of last dose
	4	Permanently discontinue	Permanently discontinue
Pneumonitis	2	Toxicity resolves to Grade 0-1	Toxicity does not resolve within 12 weeks of last dose or inability to reduce corticosteroid to 10 mg or less of prednisone or equivalent per day within 12 weeks.
	3-4	Permanently discontinue	Permanently discontinue
Renal Failure or Nephritis	2	Toxicity resolves to Grade 0-1	Toxicity does not resolve within 12 weeks of last dose or inability to reduce corticosteroid to 10 mg or less of prednisone or equivalent per day within 12 weeks.
	3-4	Permanently discontinue	Permanently discontinue
Stevens-Johnson Syndrome	3-4	Permanently discontinue	Permanently discontinue
All Other Drug-Related Toxicity ³	3 or Severe	Toxicity resolves to Grade 0-1	Toxicity does not resolve within 12 weeks of last dose or inability to reduce corticosteroid to 10 mg or less of prednisone or equivalent per day within 12 weeks.
	4	Permanently discontinue	Permanently discontinue

Note: Permanently discontinue for any severe or Grade 3 drug-related AE that recurs or any life-threatening event.

¹ For patients with liver metastasis who begin treatment with Grade 2 AST or ALT, if AST or ALT increases by greater than or equal to 50% relative to baseline and lasts for at least 1 week then patients should be discontinued.

² If symptoms resolve within one hour of stopping drug infusion, the infusion may be restarted at 50% of the original infusion rate (e.g., from 100 mL/hr to 50 mL/hr). Otherwise dosing will be held until symptoms resolve and the subject should be premedicated for the next scheduled dose; Refer to

Table – Infusion Treatment Guidelines for further management details.

³Patients with intolerable or persistent Grade 2 drug-related AE may hold study medication at physician discretion. Permanently discontinue study drug for persistent Grade 2 adverse reactions for which treatment with study drug has been held, that do not recover to Grade 0-1 within 12 weeks of the last dose.

Dosing interruptions are permitted in the case of medical / surgical events or logistical reasons not related to study therapy (e.g., elective surgery, unrelated medical events, patient vacation, and/or holidays). Subjects should be placed back on study therapy within 3 weeks of the scheduled interruption, unless otherwise discussed with the Sponsor. The reason for interruption should be documented in the patient's study record.

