- **INVESTIGATIONS**: activated partial thromboplastin time prolonged; alanine aminotransferase increased; alkaline phosphatase increased; aspartate aminotransferase increased; blood bilirubin increased; creatinine increased; GGT increased; INR increased; neutrophil count decreased; platelet count decreased; weight loss
- **METABOLISM AND NUTRITION DISORDERS**: anorexia; hypoalbuminemia; hyponatremia
- **MUSCULOSKELETAL AND CONNECTIVE TISSUE DISORDERS**: myalgia; arthralgia; arthritis; myositis; Rhabdomyolysis
 - Musculoskeletal and connective tissue disorders – Other, specify: myopathy; rejection of solid organ or tissue transplants (corneal, kidney, or liver)
- **NERVOUS SYSTEM DISORDERS** *: dizziness; dysgeusia; edema cerebral; headache; peripheral motor neuropathy; peripheral sensory neuropathy; seizures;

- Nervous system disorders – other, specify: Guillain-Barre syndrome; myasthenia gravis (MG)
- **PSYCHIATRIC DISORDERS:** confusion
- **RENAL AND URINARY DISORDERS ***: hematuria;
 - Renal and urinary disorders – other, specify: nephritis
- **REPRODUCTIVE SYSTEM AND BREAST DISORDERS ***
- **RESPIRATORY, THORACIC AND MEDIASTINAL DISORDERS ***: cough; dyspnea; pneumonitis
- **SKIN AND SUBCUTANEOUS TISSUE DISORDERS:** exfoliative dermatitis
 - All CTCAE rashes are considered expected: bullous dermatitis; erythema multiforme; erythroderma; palmar-plantar erythrodysesthesia syndrome; pruritus; rash acneiform; rash maculo-papular; skin hyperpigmentation; skin hypopigmentation; skin induration; skin ulceration; Stevens-Johnson syndrome; toxic epidermal necrolysis (TEN) ;
 - Skin and subcutaneous tissue disorders – other, specify: pemphigus; vitiligo
- **VASCULAR:** vasculitis

* In addition, the following adverse event is considered expected within all applicable SOCs:

- bleeding/hemorrhage

Table 5 Evaluating Adverse Events

Appropriately delegated study team members will evaluate all adverse events as to:

V5.0 CTCAE Grading	Grade 1	Mild; asymptomatic or mild symptoms; clinical or diagnostic observations only; intervention not indicated.
	Grade 2	Moderate; minimal, local or noninvasive intervention indicated; limiting age-appropriate instrumental ADL.
	Grade 3	Severe or medically significant but not immediately life-threatening; hospitalization or prolongation or hospitalization indicated; disabling; limiting self-care ADL.
	Grade 4	Life threatening consequences; urgent intervention indicated.
	Grade 5	Death related to AE

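### Table 3's note orders permanent discontinuation for any life-threatening event, but three of its 15 named toxicity rows let pembrolizumab continue or resume at grade 4, and no order of precedence is stated

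*Combined protocol and SAP*

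**What the plan says.** Section 5.2 allows dose holds but no dose reductions, and makes Table 3 the rule for withholding pembrolizumab. The note at the foot of the table applies to every row: "Note: Permanently discontinue for any severe or Grade 3 drug-related AE that recurs or any life-threatening event".

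Table 5 in Section 6.4 gives the meaning of CTCAE grade 4 for this trial: "Life threatening consequences; urgent intervention indicated".

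Three Table 3 rows include grade 4 and have no separate grade 4 line:

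- **Hypophysitis, grade 2-4.** The restart cell reads "Toxicity resolves to Grade 0-1. Therapy with pembrolizumab can be continued while endocrine replacement therapy is instituted".
- **Hypothyroidism, grade 2-4.** The restart cell and the discontinuation cell both say "Therapy with pembrolizumab can be continued while thyroid replacement therapy is instituted".
- **Type 1 diabetes or grade 3-4 hyperglycemia.** One cell says "Hold pembrolizumab for new onset Type 1 diabetes mellitus or Grade 3-4 hyperglycemia associated with evidence of beta cell failure" and the next says "Resume pembrolizumab when patients are clinically and metabolically stable within 12 weeks of last dose".

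The grades for all rows are listed under the column heading "Hold Treatment For Grade".

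Two other places bear on the point. Table 5, under rechallenge, requires advance approval by the clinical monitor before re-exposure after a serious event that the product may have caused, and refers for this to the protocol's dose-modification guidelines. Section 5.9 requires immediate notice to the Overall PI of unusual or life-threatening complications.

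**The concern.** A stopping rule should give one answer for one event. For a grade 4 event in any of these three rows, the row allows further dosing and the note forbids it. The trial is multicenter and open-label, so investigators at different sites could act differently in good faith. Either action could then be judged compliant or a departure from protocol, depending on which line the monitor applies.

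What is at stake is chiefly patient safety and consistent conduct. The descriptive summaries of reasons for discontinuation, compliance and exposure (Sections 12.2.7 to 12.2.9) could also carry site differences that reflect reading rather than tolerance.

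Below grade 4 there is a smaller problem. The hypophysitis and hypothyroidism rows do not state cleanly whether treatment is to be held at all.

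**Working it through.** No arithmetic beyond a row count applies. The check compares each row of Table 3 with the note and with the grade definitions in Table 5.

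**Step 1: count the rows.** Table 3 has 15 named toxicity rows plus a row for all other drug-related toxicity. These 12 named rows order permanent discontinuation at grade 4:

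- diarrhea/colitis
- AST, ALT or bilirubin
- hyperthyroidism
- Guillain-Barre syndrome (any grade)
- infusion reaction
- myocarditis
- myositis
- neuropathy
- pancreatitis
- pneumonitis
- renal failure or nephritis
- Stevens-Johnson syndrome

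The all-other row does the same. That leaves 15 − 12 = 3 named rows.

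**Step 2: set the three rows beside the note at grade 4.**

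| Row | Row's instruction at grade 4 | Note, read with Table 5 |
|---|---|---|
| Hypophysitis 2-4 | Restart at grade 0-1, or continue with endocrine replacement | Permanent discontinuation |
| Hypothyroidism 2-4 | Continue with thyroid replacement | Permanent discontinuation |
| Type 1 diabetes, or hyperglycemia 3-4 with beta cell failure | Hold, then resume when stable within 12 weeks of last dose | Permanent discontinuation |

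All three conflict. The link from grade 4 to life-threatening is not made inside Table 3; it comes from Table 5.

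**Step 3: look for a rule that settles it.**

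- Section 5.2 states no precedence between rows and note.
- Where the table intends an exception it can flag one: the AST/ALT/bilirubin row points to a footnote exception. The three rows above carry no such flag.
- The supportive-care text in Section 5.8 for these three disorders covers hormone replacement, corticosteroids and insulin. It gives no hold, resume or stop rule, and it sends the reader back to Section 5.2 for dose modification.
- The rechallenge clause in Table 5 adds an approval step but defers to the dose-modification guidelines, which are this table.

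**Step 4: check the two rows below grade 4.**

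- Hypophysitis: the restart cell has two sentences. Read in sequence, they mean hold until grade 0-1, after which ongoing hormone replacement is no bar to treatment. Read as alternatives, the second ("Therapy with pembrolizumab can be continued while endocrine replacement therapy is instituted") allows treatment without a hold. The cell does not say which.
- Hypothyroidism: grades 2-4 stand under a heading that says hold, but both action cells say therapy can be continued, and no hold is described.

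**The case against.** The best case for the plan has four parts.

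1. **Specific rows override a general note.** This is a reasonable way to read a table of guidelines, and it may be what the authors meant. But the note says any life-threatening event, the protocol states no such precedence, and the opposite reading is equally open.

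2. **Grade 4 need not mean life-threatening.** Under seriousness, Table 5 gives a second definition that turns on the investigator's view of immediate risk of death. On that definition some grade 4 events might fall outside the note. This narrows the conflict but does not remove it: an event in one of the three rows that does meet the definition still faces both instructions.

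3. **Sites do not act alone.** Life-threatening events are serious by definition, so the advance-approval clause for rechallenge and the immediate notice to the Overall PI both apply where their terms are met. This stands as a real limit on harm. It does not tell the approver which rule to apply.

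4. **The hold column is a grade key.** It also lists grades whose action is permanent discontinuation, so a grade listed there is not by itself an order to hold. This stands. It reduces the hypothyroidism point to a misleading label.

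A reader might also infer more than the text supports:

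- *That a grade 2 hypothyroidism patient faces anything from no missed dose to a 12-week hold.* The 12-week ceiling is the general limit in Section 5.2; no hypothyroidism cell invokes it, and both action cells agree on continuing.
- *That the hypophysitis cell flatly contradicts itself.* It is ambiguous, since the sequential reading is coherent.
- *That the resume text for diabetes, sitting in the discontinuation column, is a substantive error.* Hold followed by resume reads as one sequence; the placement is editorial.

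**Conclusion.** The point holds as an internal contradiction in a stopping rule. At grade 4, three of 15 named rows permit further pembrolizumab while the note forbids it, and nothing in the protocol decides between them. The conclusion rests on taking Table 5's description of grade 4 as the meaning of life-threatening in the note. On the narrower seriousness definition fewer events are affected, but the conflict remains. For the diabetes row it is confined to the events that row names.

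The hypophysitis ambiguity and the hypothyroidism column label are secondary wording faults.

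A reader might infer that the conflict alters the primary safety endpoint. The documents do not support that: Section 12.2.4.2 defines the primary safety endpoints as graded adverse events, not holds or discontinuations. There is no effect on power or sample size. The documents give no expected frequency for these events, so the number of patients affected cannot be estimated.

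**What to change.** In Section 5.2, Table 3:

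- Reconcile the note with the hypophysitis, hypothyroidism and type 1 diabetes/hyperglycemia rows at grade 4. Either name in the note any rows exempt from it, or give grade 4 its own line in those rows, as other rows do.
- Make the hold and restart columns agree for hypophysitis and hypothyroidism, so that each row states plainly whether treatment is held or continued.
- As an editorial matter, move the resume text in the diabetes row out of the discontinuation column.

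Which clinical rule applies is for the sponsor and its medical advisers to decide; this review takes no position on it.

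The cost is a table edit in one amendment and a memo to sites, with no effect on sample size or data already collected.
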